4.2. Study populations

All participants at each participating study site who have been treated with Oxbryta® (Voxelotor) or have been prescribed and will initiate treatment with Oxbryta® (Voxelotor) according to the Oxbryta® (Voxelotor) USPI will be considered for inclusion in this study.

Population	Description
Full analysis set	Participants met inclusion/exclusion criteria and signed the informed consent including screen failures (participants who did not receive Oxbryta within 6 months of the informed consent date).
Safety analysis set	Participants were in the Full analysis set and received at least one dose of Oxbryta including participants who received at least one dose of Oxbryta in C5341018 (RETRO) study.

When participants have been prescribed Oxbryta® (Voxelotor) and deemed eligible to participate in the registry study based on the inclusion/exclusion criteria, they will be enrolled in the study regardless of whether they have started taking Oxbryta® (Voxelotor). After enrollment into the study, it is recommended that the site perform the pre-Oxbryta® (Voxelotor) participant assessments as soon as possible. Once the first dose of Oxbryta® (Voxelotor) treatment has been administered, the participants will be followed for up to 5 years. Patient enrollment process flow is shown in Figure 2.

Figure 2. Enrollment Process Flow

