9.11. Statistics

9.11.1. Analysis Population

Effectiveness and safety analyses will primarily be based on the treated population, defined as all participants receiving at least one dose of Oxbryta® (Voxelotor).

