4.7.3. Analyses for Effectiveness Endpoint Measures

Since this study was not designed as the efficacy study for different indications that contribute significant information about product safety, the analyses in the SAP are considered fit-for-purpose for an abbreviated clinical study report with data scope including 1) full safety data and 2) limited efficacy data to support the benefit-risk evaluation.

Given the reporting nature of the PROMIS items, the reported PRO response was sparse. Therefore, they were excluded from the planned CSR analyses.

The analyses for effectiveness endpoints are based on full analysis set (Section 4.2). The analyses for the abbreviated CSR focus on hematologic and renal function laboratory parameters and SCD-related clinical events.

Participant disposition, non-SCD medical history, concomitant medication, study drug administration (including dosage changes initiated by the participant and by the physician), demographics and baseline characteristics will be summarized descriptively based on full analysis set.

The descriptive statistics will be provided for the following medications:

- long-acting opioids
- Erythropoiesis-stimulating agents
- Other relevant pain meds (e.g. Gabapentin, Lyrica, Cymbalta)
- SCD disease modification agents (hydroxyurea, Adakveo/crizanlizumab, L-Glutamide/levoglutamide).

The study drug administration will be categorized as 1) < 1 month, 2) >=1, <2 months, 3) < 3 months, 4) >=3 months, < 6 months, 5) >=6 months, < 9 months, 6) >=9 months, < 12

months, 7) ≥ 12 months, < 18 months, 8) ≥ 18 months, < 24 months, 9) ≥ 24 months, < 36 months, 10) ≥ 36 months, < 48 months and 11) ≥ 48 months.

The following effectiveness endpoints will be summarized descriptively:

- Change from pre-Oxbryta treatment period in the following hematologic parameters corresponding to treatment with Oxbryta® (Voxelotol):
 - Hb
 - Hemolysis measures, including % reticulocytes, absolute reticulocytes, bilirubin (total, direct, and indirect)
 - ALT and AST

Analysis: Observed and change from pre-Oxbryta treatment period on Hb, Hemolysis measures will be summarized descriptively ([Section 4.7](#)) by visit

If a queried hemolysis value remained greater than its threshold listed in the table below, the value would be deemed erroneous and excluded from the analysis,

Parameter	Threshold
Reticulocyte Count (absolute)	10,000 $10^{9}/L$
Ferritin	100,000 $\mu g/L$

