- Change from pre-Oxbryta treatment period in the following Chemistry parameters corresponding to treatment with Oxbryta® (Voxelotol):
 - Ferritin

Analysis: Observed and change from pre-Oxbryta treatment period on ferritin will be summarized descriptively ([Section 4.7](#)) by visit.

- Change from pre-Oxbryta® (Voxelotol) treatment period in renal function:
 - Creatinine (Serum)
 - Albuminuria (urine albumin/creatinine ratio [ACR])
 - Hemoglobinuria (urine dipstick positive for blood +1 or greater and ≤ 2 RBC by high power field)
 - Serum cystatin C
 - Estimated eGFR calculated using the CKD-EPI equation

Analysis: Observed and change from pre-Oxbryta treatment period on Creatinine (Serum), Albuminuria, Hemoglobinuria, Serum cystatin C and eGFR will be summarized descriptively ([Section 4.7](#)) by visit

- Rate of SCD complications including acute pain crisis, acute chest syndrome

(ACS), priapism, stroke, and transient ischemic attack (TIA), chronic or end stage kidney disease, iron overload, leg ulcers, cardiac malfunction, and pulmonary hypertension (PH) and RBC transfusions.

Analysis:

The number and percentage of participants with SCD complications including acute pain crisis, ACS, priapism, stroke, chronic or end stage kidney disease iron overload, leg ulcers, cardiac malfunction and PH and RBC transfusions will be summarized by SOC and PT throughout the treatment period.

The annualized incidence rate of SCD complications including acute pain crisis, ACS, priapism, stroke, chronic or end stage kidney disease iron overload, leg ulcers, cardiac malfunction and PH and RBC transfusions will be summarized by SOC and PT throughout the treatment period.

- **PGIC**

PGIC includes 7 response categories: Very much improved, much improved, minimally improved, no change, minimally worse, much worse and very much worse.

Analysis: The PGIC will be summarized as numbers and percentages by visit for each response category.

- **CGIC**

CGIC includes 7 response categories: Very much improved, much improved, minimally improved, no change, minimally worse, much worse and very much worse.

Analysis: The CGIC will be summarized as numbers and percentages by visit for each response category.

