6. APPENDICES

6.1. Appendix A: List of tables

Table/Listing	Title	Endpoint
Table 15.1.1	Summary of Participant Disposition - Full Analysis Set	Disposition
Table 15.1.2	Demographics and Baseline Characteristics - Full Analysis Set	Baseline
Table 15.1.3	Medical History – Full Analysis Set	Medical history

Table 15.1.4	Study Drug Administration - Safety Analysis Set	Exposure
Table 15.1.5	Study Drug Administration and Dosage Changes Initiated by the Physician - Safety Analysis Set	Exposure
Table 15.2.1	Change in Hematologic Laboratory -Hb Tests by Visit - Full Analysis Set	Effectiveness
Table 15.2.2	Change in Hematologic Laboratory -Hemolysis measures by Visit - Full Analysis Set	Effectiveness
Table 15.2.3	Change in Chemistry Laboratory - Chemistry measures by Visit - Full Analysis Set	Effectiveness
Table 15.2.4	Change in Renal Function Laboratory Tests by Visit - Full Analysis Set	Effectiveness
Table 15.2.5	Summary of SCD Complications-Full Analysis Set	Effectiveness
Table 15.2.5.1	Summary of Transfusions -Full Analysis Set	Effectiveness
Table 15.2.6	Annualized Incidence Rate of SCD Complications - Safety Analysis Set	Effectiveness
Table 15.2.6.1	Annualized Incidence Rate of Transfusions - Safety Analysis Set	Effectiveness
Table 15.2.7	Summary of Patient Global Impression of Change (PGIC) – Full Analysis Set	HRQoL
Table 15.2.8	Summary of Clinical Global Impression of Change (CGIC) – Full Analysis Set	HRQoL
Table 15.3.1	Treatment Emergent Adverse Events by System Organ Class and Preferred Term by Severity - Safety Analysis Set	Safety
Table 15.3.2	Treatment Related Treatment Emergent Adverse Events by System Organ Class and Preferred Term by Severity- Safety Analysis Set	Safety

Table 15.3.3	Treatment Emergent Serious Adverse Events by System Organ Class and Preferred Term by Severity - Safety Analysis Set	Safety
Table 15.3.4	Pregnancy Outcomes and Fertility listings - Safety Analysis Set	Safety
Table 15.3.5	Individual Listings of Deaths- Safety Analysis Set	Safety
Table 15.3.6	Listing of AEs Leading to Discontinuation of the Study - Safety Analysis Set	Safety
Table 15.3.7	Individual Listing of SAEs - Safety Analysis Set	Safety
Table 15.4	Listing of Concomitant Medication - Safety Analysis Set	Concomitant Medication
Table 15.5.1	Annualized Incidence Rate of Acute Pain Crisis – Safety Analysis Set (With Chronic Pain)	Subgroup
Table 15.5.2	Annualized Incidence Rate of Acute Pain Crisis – Safety Analysis Set (Without Chronic Pain)	Subgroup

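### The SAP moves effectiveness from the protocol's treated population to a Full Analysis Set that includes undosed screen failures, splits complications and transfusions over two populations, and may dilute two percentage tables

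*SAP*

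**What the plan says.** Protocol 9.11.1 states: "Effectiveness and safety analyses will primarily be based on the treated population, defined as all participants receiving at least one dose of Oxbryta". The protocol abstract says the same.

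SAP 4.2 defines two sets. The Full Analysis Set is everyone eligible and consented, "including screen failures (participants who did not receive Oxbryta within 6 months of the informed consent date"). The Safety Analysis Set is narrower: "Participants were in the Full analysis set and received at least one dose of Oxbryta", with doses taken in the earlier RETRO study also counting. The Safety set is in substance the protocol's treated population.

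SAP 4.7.3 states: "The analyses for effectiveness endpoints are based on full analysis set (Section 4.2"). For SCD complications and RBC transfusions it asks for two summaries, the number and percentage of participants and the annualized rate. Both "will be summarized by SOC and PT throughout the treatment period".

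Appendix A assigns these two summaries to different sets. Table 15.2.5 is titled "Summary of SCD Complications-Full Analysis Set", while Table 15.2.6 is titled "Annualized Incidence Rate of SCD Complications - Safety Analysis Set". Transfusions are divided in the same way between Tables 15.2.5.1 (Full) and 15.2.6.1 (Safety).

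**The concern.** The protocol and the SAP name different populations for effectiveness, and the SAP gives no reason. The wider set can hold people who never took the drug, yet the summary asked of it concerns the treatment period. If those people enter the denominator with no events, complications and transfusions on the drug look rarer than they were. The error can only run in that direction, and the SAP says the report is meant to support a benefit-risk evaluation.

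The split is a problem even if few people were undosed. The percentage table and the rate table for one endpoint need not describe the same participants, and the rate tables contradict the SAP's own statement that effectiveness uses the Full set. A programmer cannot follow both the text and the table titles.

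**Working it through.** The plan gives no figure to reproduce. SAP 4.5 says there is no formal sample size calculation, and no count of undosed participants is given. The check compares the passages and then works out the size under stated assumptions.

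**1. Is a never-dosed person within the summary?** SAP 4.7.1 starts the post-Oxbryta period at the first dose. SAP 4.3 also anchors the pre-Oxbryta window and age to the first dose. For a never-dosed person all three are undefined, so no treatment-period percentage applies to that person.

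**2. Effect on the percentages.** Let p be the true percentage among dosed participants and f the share of the Full set never dosed. If the never-dosed count as event-free:

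reported percentage = p × (1 - f); loss in points = p × f.

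For illustration, take a Full set of 500 (the planned enrolment) and assume p = 40%. The values of f are also assumptions.

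| f | Never dosed | Dosed | With event (40% of dosed) | Reported on Full set | Loss in points |
|---|---|---|---|---|---|
| 2% | 10 | 490 | 196 | 196/500 = 39.2% | 0.8 |
| 5% | 25 | 475 | 190 | 190/500 = 38.0% | 2.0 |
| 10% | 50 | 450 | 180 | 180/500 = 36.0% | 4.0 |
| 20% | 100 | 400 | 160 | 160/500 = 32.0% | 8.0 |

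The relative reduction equals f, whatever p is.

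**3. Effect on post-dose annualized rates.** SAP 4.7 divides total events by total patient-years. A never-dosed person adds no post-dose events and no post-dose time. Assume f = 10%, 2 events per year and 2 years of follow-up for each of the 450 dosed: 1,800 events over 900 patient-years is 2.0 per year. Adding 50 people with zero time leaves it at 2.0.

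**4. Effect on PGIC and CGIC by visit.** SAP 4.7 calculates percentages over non-missing data. Assume 60% of the 450 dosed respond (270) and 40% of responders improve (108): 108/270 = 40.0% in either set.

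**5. Effect on laboratory changes.** A change from the pre-Oxbryta period needs a post-dose value, which a never-dosed person does not have. Nothing moves.

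**6. Where else the populations disagree.**

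| Analysis | Full set in | Safety set in |
|---|---|---|
| Chronic pain subgroups | SAP 4.2.1 | Tables 15.5.1, 15.5.2 |
| Hb-increase subgroups | SAP 4.2.1 and 4.7.5 | Tables 15.5.3, 15.5.4 |
| Two VOC populations | SAP 4.2.1, items 3 and 4 | SAP 4.7.5 |
| Study drug administration | SAP 4.7.3 | Tables 15.1.4, 15.1.5 |
| Concomitant medication | SAP 4.7.3 | Table 15.4 |

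These are conflicts of labelling. They add no dilution of their own.

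**The case against.** The strongest reply is that the SAP may already exclude these people. Its general rule takes percentages over participants with available data, and a never-dosed person has no treatment-period data. On that reading the denominators of Tables 15.2.5 and 15.2.5.1 hold only dosed participants and there is no dilution. This stands in part: it makes the dilution conditional. It does not remove the problem, because the SAP does not apply the rule to event tables, where the absence of a record is ordinarily read as no event, and the titles name the Full set.

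Second, the protocol says only that analyses are primarily on the treated population, and the SAP's analyses are descriptive, for an abbreviated report. That permits a supplementary analysis on a wider set. It does not explain why the wider set has become the stated basis for effectiveness.

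A reader might infer two stronger things, and the documents support neither. One is that undosed people distort the effectiveness results generally. Steps 3 to 5 show that post-dose rates, by-visit PGIC and CGIC percentages and laboratory changes are the same in either set. The other is that the understatement equals the screen-failure share. A screen failure is someone not dosed within 6 months of consent, so a person who starts in month 7 meets that definition and also qualifies for the Safety set. Only the never-dosed share matters, and it is a relative reduction: at 10%, a true 40% loses 4 points, not 10.

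Nothing in the documents supports the upper end of the assumed range. The registry also admits people already on the drug and transfers from RETRO, who are dosed by definition.

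**Conclusion.** The conflict between protocol 9.11.1 and SAP 4.7.3 is plain in the text, and so is the split of SCD complications and transfusions between the Full and Safety sets. Neither depends on how many people were undosed.

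The numerical consequence is narrower. It can reach only the percentages in Tables 15.2.5 and 15.2.5.1, and only if never-dosed participants are counted as event-free. In that case the understatement is p × f: from 0.8 to 8.0 points for an assumed true 40% and an assumed never-dosed share of 2% to 20%. The true share is not in the documents, and if few were undosed the effect is small. The SAP should be corrected on this point because the right set is already defined and any error would favour the drug.

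**What to change.** - In SAP 4.7.3, base post-dose effectiveness analyses on the Safety (treated) set, as the protocol does.
- Retitle Tables 15.2.5 and 15.2.5.1 to the Safety set, so that percentages and rates describe the same people. For consistency with the protocol, retitle Tables 15.2.1 to 15.2.4, 15.2.7 and 15.2.8 as well; their on-treatment results will not change.
- Align SAP 4.2.1, 4.7.3, 4.7.5 and Appendix A to the Safety set for the subgroups, the two VOC populations, study drug administration and concomitant medication.
- Leave the Full Analysis Set for disposition, demographics and medical history, where no fault is shown.

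The cost is SAP wording and table titles. No new data or new analysis set is needed.

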4.2.1. Subgroups

- 1) Chronic pain:
 - a. Full analysis set for participants with chronic pain
 - b. Full analysis set for participants without chronic pain

Participants with chronic pain are defined to have at least one of following criteria during pre-Oxbryta or post-Oxbryta:

- SCD complications page: Avascular Necrosis, Chronic Pain; OR
- Non-SCD medical history page: Arthralgia, Arthritis, Neuralgia, Osteoarthritis, Osteonecrosis, Osteoarthritis, Rheumatoid arthritis, Spinal osteoarthritis; OR
- Concomitant medications page: BACLOFEN, GABAPENTIN, MELOXICAM, PREGABALIN, all “BUPRENORPHINE”, DULOXETINE, DULOXETINE HYDROCHLORIDE, METHADONE, METHADONE HYDROCHLORIDE, PREGABALIN.

- 2) Maximum increase from Pre-Oxbryta in Hb
 - a. Full analysis set for participants with > 1 g/dL maximum increase from Pre-Oxbryta in Hb during the study period

b. Full analysis set for participants with ≤ 1 g/dL maximum increase from Pre-Oxbryta in Hb during the study period

3) Full analysis set where participants had a non-missing Pre-Oxbryta SCD complication will be included in the analysis.

4) Full analysis set where participants who had a non-missing Pre-Oxbryta SCD complication or participants who had an adverse event reported in Pre-Oxbryta or Post-Oxbryta will be included in the analysis.

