7.1. Introduction

7.1.1. Disease Background

Sickle cell disease (SCD) is an inherited blood disorder caused by a point mutation in the β globin gene resulting in the formation of sickle hemoglobin (HbS), which polymerizes in the deoxygenated state and leads to red blood cell (RBC) sickling. The disease is marked by the pathophysiologic features of hemolytic anemia, vaso-occlusion, and progressive end-organ damage, with a clinical course characterized by life-long disability and early death.^{2,4} In addition to unpredictable and recurrent vaso-occlusive pain episodes, hemolytic anemia directly damages blood vessels, resulting in a systemic vasculopathy that leads to chronic and progressive tissue and organ injury.³ With improved survival in children, the natural history of SCD has shifted from a disease of childhood to a chronic, debilitating disease of young and middle-aged adults. Cumulative injury to multiple organ systems from repeated episodes of RBC sickling, vaso-occlusion, and chronic hemolytic anemia exert a high clinical burden in the aging adult, significantly impacting quality of life (QoL) and overall functioning.⁷

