4.7. Statistical methodology and analyses

The following general analysis will be followed for this study, unless otherwise specified.

Unless otherwise specified, continuous/quantitative variables will be summarized using descriptive statistics which will include the number of participants with data to be summarized (n), mean, standard deviation (SD), median, first and third quartile (Q1, Q3), minimum, maximum, and the number of missing observations. Minimum and maximum will be reported with the same number of decimal places as collected in raw data, while mean, median, Q1, Q3 will be reported with one extra decimal place, and SD will be reported with two extra decimal places. Descriptive statistics for categorical/qualitative variables will be presented with number of participants and percentage (%) of participants in each category.

Percentages will not include the missing category and will be calculated over the number of participants with available (non-missing) data. A category with a zero count will be presented as “0” and a category with a 100 percentage will be displayed as “100”.

The annualized incidence rate is defined as total numbers of a given event for all participants divided by the total patient-year where the total patient-year is defined as the sum of total duration (years) as defined in the Section 4.7.1 for all participants.

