4.7.5. Subgroup analyses

Analysis: The annualized incidence rate (per patient year) of rate of ‘Acute Pain Crisis’ (SCD Complications) will be performed by Pre-Oxbryta and Post-Oxbryta.

Analysis subgroups:

- Chronic pain
 - a. participants with chronic pain
 - b. participants without chronic pain
- Maximum increase from Pre-Oxbryta in Hb
 - a. Full analysis set for participants with > 1 g/dL maximum increase from Pre-Oxbryta in Hb
 - b. Full analysis set for participants with <= 1 g/dL maximum increase from Pre-Oxbryta in Hb

Analysis: Annualized incidence VOC rate for pre-Oxbryta and post-Oxbryta will be reported.

The VOC event for Pre-Oxbryta is defined as 1) SCD complication with ‘Acute Pain Crisis’ in the Pre-Oxbryta SCD complication page or 2) any qualifying complications from SCD AE prior to Treatment Start Date.

The VOC event for Post-Oxbryta is defined as any qualifying complications from SCD AE on or after the treatment start date.

The qualifying complications from SCD AE are those that met at least one of the following two conditions:

- AE preferred term (AEDECOD) to be 'Sickle cell anaemia crisis';
- type of complications (CMPTYP) is 'Acute Pain Crisis'

- 1) Analysis population: Safety analysis set where participants had a non-missing Pre-Oxbryta SCD complications will be included in the analysis.
- 2) Analysis population: Safety analysis set where participants who had a non-missing Pre-Oxbryta SCD complications or participants who had an adverse events reported in Pre-Oxbryta or Post-Oxbryta will be included in the analysis.

Analysis: The annualized VOC incidence rate (per patient year) will be performed by Pre-Oxbryta and Post-Oxbryta.

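### The chronic-pain subgroup is defined partly from post-dose records, so its before/after crisis rates can move with no drug effect; define it from pre-dose data and caution about regression to the mean

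*SAP*

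**What the plan says.** - **Membership.** SAP 4.2.1: "Participants with chronic pain are defined to have at least one of following criteria during pre-Oxbryta or post-Oxbryta". The criteria sit on three case report form pages. The first is "SCD complications page: Avascular Necrosis, Chronic Pain; OR". The second is a list of joint and nerve disorders on the non-SCD medical history page. The third begins "Concomitant medications page: BACLOFEN, GABAPENTIN, MELOXICAM, PREGABALIN, all" and goes on to buprenorphine products, duloxetine and methadone. No start-date limit is given.
- **Analysis.** SAP 4.7.5 says that the annualized acute pain crisis rate "will be performed by Pre-Oxbryta and Post-Oxbryta", separately for participants with and without chronic pain. Appendix A assigns Tables 15.5.1 and 15.5.2. (SAP 4.2.1 and the table titles name different analysis sets; that is a separate matter.)
- **Rate.** SAP 4.7 pools: "total numbers of a given event for all participants divided by the total patient-year".
- **Windows.** The pre-dose period is 12 months (SAP 4.3 and 4.7.4). The post-dose period runs up to 5 years (SAP 4.3), or to end of treatment or end of study (SAP 4.7.1).
- **What is absent.** SAP 4.2.1, 4.7.5 and the table list contain no baseline-only version, no sensitivity analysis and no caution. No test is planned.

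**The concern.** A participant with no qualifying entry at first dose who later has many crises, and is then given a chronic pain diagnosis or a listed medicine, is counted with all their crises in the *with* group. The *without* group keeps those who stayed free of such entries for the whole of follow-up. Selecting on the post-dose period in this way can lower the post-dose rate in *without* and raise it in *with*. That would look like benefit in one group and a differing effect between groups, with no drug effect in either.

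A link between crises and later qualifying entries is plausible. The Protocol's disease background describes "Cumulative injury to multiple organ systems from repeated episodes of RBC sickling, vaso-occlusion, and chronic hemolytic anemia", and SAP 4.7.3 groups gabapentin and similar products as pain medicines. An association is all the argument needs.

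The tables feed an abbreviated report whose limited efficacy data are meant to support the benefit-risk evaluation (SAP 4.7.3). A group that is known only after follow-up cannot describe who, at first dose, went on to have fewer crises.

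**Working it through.** The plan gives no crisis rates and no formal sample size calculation (SAP 4.5), so there is no stated figure to reproduce. The check asks what the rule does when the drug does nothing, so the true post/pre ratio is 1.00.

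**1. Where the qualifying time lies.** With 5 years of follow-up, 5/(5+1) = 83% of the time in which an entry can arise is post-dose. With 6 months it is 0.5/(0.5+1) = 33%. Membership leans on post-dose data, and more so the longer a person is followed.

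**2. Hand calculation, only post-dose crises lead to entries.** Assumptions, not from the documents: crisis rate λ per year, exponential with mean 2 (gamma shape 1) and stable within person; post-dose time T uniform on 0.5 to 4 years; each post-dose crisis leads to a qualifying entry with probability p = 0.05. A person stays in *without* with probability exp(−pλT) and then has expected post-dose crises λT(1−p). With c(T) = 1 + 2pT = 1 + 0.1T and integrals over 0.5 to 4:

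- pre rate = 2·∫c⁻²dT / ∫c⁻¹dT = 2 × 2.381/2.877 = 1.655
- post rate = (1−p)·2·∫T·c⁻²dT / ∫T·c⁻¹dT = 0.95 × 2 × 4.959/6.232 = 1.512
- ratio = 1.512/1.655 = 0.91

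The simulation adds 30% with chronic pain at first dose, assigned at random, and lets each person's rate vary between periods (log-SD 0 to 0.5). Ratios in *without*:

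| p | post/pre ratio |
|---|---|
| 2% | 0.92 to 0.96 |
| 5% | 0.83 to 0.91 |
| 10% | 0.73 to 0.84 |

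In *with* they were 1.04 to 1.13.

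**3. Same inputs, but pre-dose crises also lead to entries.** Now c(T) = 1 + 2p(1+T) = 1.1 + 0.1T, and the factor (1−p) applies to both periods:

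- pre rate = 0.95 × 2 × 2.029/2.657 = 1.451
- post rate = 0.95 × 2 × 4.251/5.773 = 1.399
- ratio = 1.399/1.451 = 0.96

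The factor (1−p) cancels. What remains here comes from follow-up that differs between people. Across p = 2% to 10%, log-SD 0 or 0.5, and with or without a random 30% background, simulation gave 0.88 to 0.98 in *without* (a false fall of 2% to 12%) and 0.97 to 1.05 in *with*.

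**4. A different model.** Assumptions: mean 3 crises per year, log-scale SD 0.8, and a yearly chance of a qualifying entry averaging about 19% and rising with current pain. Ratios in *without* under the SAP rule:

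| Setting | Correlation 0.2 | 0.5 | 0.8 |
|---|---|---|---|
| Pain varies yearly, 5 years post | 0.98 | 0.95 | 0.95 |
| Same, half of pre-dose entries unrecorded | not run | 0.87 | 0.91 |
| One pain level per period, 5 years post | 0.73 | 0.81 | 0.91 |
| One pain level per period, 2 years post | 0.90 | 0.93 | 0.97 |

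**5. When the bias vanishes or reverses.** In the second model, equal 1-year windows with equal recording give 1.00. So do pain fixed for life and entries unrelated to crises. If pre-dose pain is first recorded after dosing, the ratio in *without* is 1.05 to 1.08, a false rise.

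**6. Baseline-only definition.** Under the step 3 inputs, *without* is 1.02 to 1.21 and *with* is 0.66 to 0.96. In the second model they are 1.05 to 1.22 and 0.58 to 0.90. This is regression to the mean: people who qualify because of a bad year before dosing tend to improve, and the others drift up.

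**The case against.** The strongest reply is that the obvious repair can leave a larger distortion than the one it removes. Step 6 bears this out: the false fall moves from *without* to *with*, and the gap between the groups usually widens. A reader might infer that a baseline-only definition brings both ratios to 1.00. That holds only if baseline chronic pain is assigned without regard to recent crises, which is an assumption and not a result.

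Second, the direction is not fixed. A reader might infer that the present rule must favour the drug in *without*. The documents do not support that. The rule also removes people with high pre-dose pain, which offsets the post-dose selection, and step 5 shows settings with no bias or the opposite sign.

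Third, nothing in either document says that the listed entries are made because pain worsened after first dose. Acute pain crisis is not itself a criterion. The medical history page is scheduled only before treatment (Protocol Appendix 1), so one of the three sources is already largely pre-dose.

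Fourth, these are descriptive tables in an abbreviated report, and Protocol 9.13 concedes that comparisons of outcomes are open to several sources of bias.

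All four stand, and they limit the size, certainty and urgency of the point. They do not remove it: membership still depends on the outcome period and on follow-up length, and no section of the SAP says so. The general caution in Protocol 9.13 does not alert a reader of Table 15.5.2 that its group was chosen using post-dose records.

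**Conclusion.** The point holds as a weakness that should be fixed, not as one that invalidates the report. The text of SAP 4.2.1 and 4.7.5 is clear, and the dependence on post-dose data needs no assumption. The size does. With no drug effect, a false fall in *without* of about 2% to 12% is plausible when pre-dose and post-dose crises can both lead to entries. It reaches about 27% if only post-dose crises do, or if each period has its own weakly related pain level and follow-up is 5 years. These figures rest on assumed crisis rates, persistence of pain, recording and follow-up, none of which the documents give.

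A reader might infer from differing ratios in Tables 15.5.1 and 15.5.2 that the drug works differently with and without chronic pain. Neither the present rule nor a baseline rule supports that reading: the first selects on post-dose records, and the second leaves regression to the mean.

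**What to change.** In SAP 4.2.1, for Tables 15.5.1 and 15.5.2:

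1. Define chronic pain from entries on all three pages with onset or start before the first dose.
2. State how partial or missing onset and start dates are handled. SAP 4.6 covers adverse event start dates and end-of-study and end-of-treatment dates, but not medication or history start dates.
3. Note that the medication look-back is 12 months before screening, not before first dose (Protocol 9.5.2). For participants already on drug at consent, medicines stopped before that window may be missed. For those enrolled more than 12 months after first dose, the window contains no pre-dose time.
4. Keep the pre-or-post rule only as a labelled sensitivity analysis.
5. Report the number who newly qualify after first dose as a descriptive result.
6. State beside the tables that pre/post ratios in baseline-defined groups remain subject to regression to the mean (a false fall in *with*, a false rise in *without*), so differences between the groups are not evidence of effect modification.

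The cost is SAP wording, a date filter and a date rule, with no new data. The *with* group becomes smaller: in the second model (yearly-varying pain, correlation 0.5, 5 years) it goes from 68% to 19% of participants. Regression to the mean is not removed, which is why the note in item 6 belongs with the new definition.
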